**Support from managers and from family/friends**

A 2 item questionnaire asks “During the COVID-19 pandemic, how well supported have you been by your supervisors/managers?” The response is rated as “not at all”, “quite a bit”, “moderately”, “quite a bit”, or “extremely” ([name], 2021, personal communication). The second questionnaire items asks “how well supported have you been by your family/friends?” rated using the same response format.

**Intention to leave job (Cohen, 1998)**

3 items are used to assess participants’ intention to leave their job e.g. “I think a lot about leaving the job”, each rated from 1 (strongly agree) to 5 (strongly disagree). The total score ranges 3 to 15, with a lower score indicating stronger intention to leave the job.

**Changes to health and work**

At week 4 and 8 participants in both arms complete a 6-item questionnaire. This questionnaire will be used to assess the occurrence of any new traumatic events, any additional stressful life events (e.g. relationship problems, financial problems), new treatments received, social support received, changes to the job, or changes to the number of hours worked per week since the last assessment.

Note: Changes to health and work questionnaire is not required to be completed at baseline.

## 5.6 Intervention procedures

After completing baseline questionnaires, participants will be sent information explaining what will happen next in the study. This information will differ according to whether they have been allocated to the immediate intervention or delayed intervention arm. Participants in the immediate intervention arm will be contacted to arrange a time to go through the digital intervention instructions with them for the first time (see below). They will then have access to the digital intervention for 4 weeks. Participants in the delayed intervention arm will be asked to complete the online intrusive memory diary and intrusive memory ratings using ePRO (as for the run-in week, section 5.4), at week 4. They will then be contacted by a researcher to arrange a time to go through the digital intervention instructions with them (as in the immediate intervention group). They will have access to the digital intervention for the next 4 weeks.

### 5.6.1 Digital intervention

The brief, digital intervention is a 30-minute, single-session task completed by the participant on their smart phone or other internet-enabled device. It includes animated videos to explain what the intervention is and how to do it, and takes participants through each step one at a time. The intervention will be delivered on a secure web platform used for clinical self-management of health in general practice (i-spero®). Participants will be sent a unique registration code to create a personal, password-protected user account to access the intervention.

Participants will be contacted by the researcher to arrange a video call to run through the intervention with them for the first time. The investigator team may audio-record the guided intervention sessions using Microsoft Teams for training and treatment fidelity assessment purposes. For those in the immediate intervention arm, this will be as soon as possible after completing baseline questionnaires. For those in the delayed intervention arm, this will be approximately 4 weeks after completing baseline questionnaires. During this session, the participant will be asked to briefly list the different intrusive memories they have and choose the one they wish to target first (“list of intrusive memories (hotspots)” – see below). They will then be asked to complete the intervention, which includes several key components: a) the participant is asked to briefly bring to mind the intrusive image as a reminder to the specific memory, b) they receive instruction on how to play the computer game Tetris using “mental rotation”, and c) they are asked to play Tetris using mental rotation for at least 20 minutes. During the intervention, participants

are asked to rate how distressed they are feeling on 3 occasions ("distress rating" – see below), to rate the vividness of the image that is brought to mind ("reactivation vividness rating" – see below), and to rate how much they were able to follow mental rotation instructions ("mental rotation rating" – see below), to assess adherence to the instructions. After this first session, participants may use the intervention as many times as they like over the next 4 weeks (e.g. to target other intrusive memories or those that recur), either on their own or with the option of researcher support. Intervention use and compliance will be assessed and monitored.

**Within-intervention measures:****List of intrusive memories (hotspots)**

Participants are asked to briefly list the content of the different intrusive memories they are having i.e. a few words to describe the image that pops up for each e.g. "seeing the patient's face". They are asked to move quickly from one to the next, and not to think about their memories in any detail.

**Distress rating**

Participants are asked to rate how distressed they are feeling right now, on a 11-point rating scale from 0 = not at all distressed to 10 = extremely distressed. This measure is given before the memory reminder cue, after the memory reminder cue, and after playing Tetris.

**Reactivation vividness rating**

After the memory reminder cue, participants are asked to rate how vividly they saw the intrusive memory in their mind, rated as 1 = no image at all, 2 = vague and dim, 3 = moderately clear and vivid, 4 = clear and reasonably vivid and 5 = perfectly clear and as vivid as normal vision.

**Mental rotation rating**

After playing Tetris, participants are asked to rate how closely they were able to follow instructions i.e. plan ahead and visualise where to play the blocks coming up next, on a 11-point rating scale from 0 = not at all closely to 10 = extremely closely.

**Record of intrusive memories**

During the 4-week period participants have access to the intervention, they will be asked to complete a daily record of their intrusive memories using the same web platform as the intervention (i-spero®), to identify which intrusive memories they have had (in addition to how many). The purpose of recording intrusive memories in this way is to identify when participants might benefit from repeating the intervention, i.e. when they have intrusive memories. If they record the occurrence of intrusive memories, they will be given the option of repeating the intervention to target those intrusive memories.

**5.6.2 Intervention accessibility post trial end date**

The digital intervention will be made available to all participants who have requested to keep having continued access to the intervention after the trial's end date (please refer to section 5.8 of the protocol for more information on end of trial definition). Those participants who have requested to keep their access will have continued access to non-guided version of the intervention for a period of 12 months after they have completed the trial.

## 5.7 In study procedures

### 5.7.1 Week 1 (D1 to D7)

Immediate Intervention Arm:

- On Day 1 the participant meets with the researcher (virtual visit) to complete the intervention for the first time. Each time the participant completes the intervention they will choose an intrusive memory to work on, complete distress ratings (x3), play Tetris® using mental rotation, complete a reactivation vividness rating and a mental rotation rating (for further detail of the intervention see section 5.6.1 Digital intervention). Following the completion of the first intervention, participants in this arm will have continued access to the intervention for 4 more weeks (D28).

All participants in the immediate intervention arm will use i-spero® to complete a daily record of intrusive memories for 4 weeks and access the intervention.

Delayed Intervention Arm:

- During week 1 participants in the delayed intervention arm are not required to complete any procedures.

### 5.7.2 Week 2&3 (D8 to D21)

Immediate Intervention Arm:

- During week 2 and 3 participants in the immediate intervention arm will have continuous access to the intervention on i-spero®.

Delayed Intervention Arm:

- During week 2 and 3 participants in the delayed intervention arm are not required to complete any procedures.

### 5.7.3 Week 4 (D22 to D28)

Immediate Intervention Arm:

- All participants in the immediate intervention arm will be asked to complete the online questionnaires at the end of week 4 (D28), including IES-R, PCL-5 4-item version, GAD-2, PHQ-2, SCI, PSYCHLOPS, WHODAS, EQ-5D-5L, Number of sick days, Scale of Work Engagement and Burnout (SWEBO), Intention to leave job, in addition to changes to health and work on ePRO.

- All participants in the immediate intervention arm will have continuous access to the intervention and at the end of week 4 (D28) will be asked to complete the daily intrusive memory diary during week 4 (D22 to D28) on a daily basis followed by intrusive memory ratings at the end of week 4 (D28) on ePRO.

Delayed Intervention Arm:

- All participants in the delayed intervention arm will be asked to complete the daily intrusive memory diary during week 4 (D22 to D28) on a daily basis followed by intrusive memory rating at the end of week 4 (D28) on ePRO.
- All participants in the delayed intervention arm will be asked to complete the online questionnaires at the end of week 4 (D28) including IES-R, PCL-5 4-item version, GAD-2, PHQ-2, SCI, PSYCHLOPS, WHODAS, EQ-5D-5L, Number of sick days, Scale of Work Engagement and Burnout (SWEBO), Intention to leave job, in addition to changes to health and work on ePRO.

#### 5.7.4 Week 5,6 & 7 (D29 to D49)

Immediate Intervention Arm:

- All participants in the immediate intervention arm are not required to complete any procedures during week 5, 6 and 7, but continue to have access to the intervention on i-spero® (for optional use).

Delayed Intervention Arm:

- On Day 1 of Week 5 (D29+7 days), the participant meets with the researcher (virtual visit) to complete the intervention for the first time. Each time the participant completes the intervention they will choose an intrusive memory to work on, complete distress ratings (x3), play Tetris® using mental rotation, complete a reactivation vividness rating and a mental rotation rating (for further detail of the intervention see section 5.6.1 Digital intervention). Following the completion of the first intervention, participants in this arm will have continued access to the intervention for 4 more weeks (D56+7 days). All participants in the delayed intervention arm will use i-spero® to complete a daily record of intrusive memories for 4 weeks (from Week 5 to 8+7 days inclusive) and access the intervention.

#### 5.7.5 Week 8 (D50 to D56)

Immediate Intervention Arm:

- All participants in the immediate intervention arm will be asked to complete the intrusive memory rating at the end of week 8 (D56).
- All participants in the immediate intervention arm will be asked to complete the online questionnaires at the end of week 8 (D56), including IES-R, PCL-5 4-item version, GAD-2, PHQ-2, SCI, PSYCHLOPS, WHODAS, EQ-5D-5L, Number of sick days, Scale of

Work Engagement and Burnout (SWEBO), Intention to leave job in addition to changes to health and work on ePRO.

Delayed Intervention Arm:

- All participants in the delayed intervention arm will be asked to complete the online questionnaires at the end of week 8 (D56+7 days), including IES-R, PCL-5 4-item version, GAD-2, PHQ-2, SCI, PSYCHLOPS, WHODAS, EQ-5D-5L, Number of sick days, Scale of Work Engagement and Burnout (SWEBO), Intention to leave job, in addition to changes to health and work on ePRO.
- All participants in the delayed intervention arm will have continuous access to the intervention and the record of intrusive memories at the end of week 8 (D56+7 days) will be asked to complete the daily intrusive memory diary during week 8 (D50 to D56) on a daily basis followed by intrusive memory ratings at the end of week 8 (D56) on ePRO.

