- Participants in the immediate intervention arm will be contacted immediately by a researcher to arrange a video call to go through the brief digital intervention for the first time with researcher support (the guided session: Day 1). The brief digital intervention is a c. 30-minute, single session task completed by the participant on their smart phone or other internet enabled device delivered on a secure web platform

used for clinical self-management of health in general practice (i-spero®). Participants in this arm will have continuous access to the intervention over the next 4 weeks (Day 1-28) and can use the intervention either on their own or with the option of researcher support. As part of the intervention, participants complete a daily record of their intrusive memories in i-spero® to identify which intrusive memories they have had, and therefore which to target with the intervention. In week 4 (Day 22-28), they will be asked to complete a daily intrusive memory diary and intrusive memory rating questionnaire in ePRO (identical to the run-in week) to assess how many intrusive memories they had each day.

- Participants in the delayed intervention arm will be asked to complete the online intrusive memory diary and intrusive memory rating questionnaire using ePRO during week 4 (Day 22 to 28), to assess how many intrusive memories they had each day. The online intrusive memory diary completed during week 4 will be the same as the intrusive memory diary completed by all participants in the run-in week. After these first 4 weeks, they will be contacted by a researcher to arrange a video call to go through the brief digital intervention for the first time (as in the immediate intervention group, i.e. the guided session: Day 29+7 days). Participants in the delayed intervention arm will have continuous access to the intervention over the next 4 weeks (Day 29 to 56+7 days) and can use the intervention either on their own or with the option of researcher support. As part of the intervention, participants complete a daily record of their intrusive memories to identify which intrusive memories they have had, and therefore which to target with the intervention. In week 8 (Day 50 to 56 +7), they will be asked to complete a daily intrusive memory diary and intrusive memory rating in ePRO (identical to the run-in week) to assess how many intrusive memories they had each day.

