Participants in both arms will be asked to complete outcome questionnaires using ePRO at 4 weeks (Day 28) and 8 weeks (Day 56). They will also be asked to complete an online feedback questionnaire about their experience of using the intervention and they will be given the option of completing a qualitative interview with a researcher via audio or video call. This will be completed after week 4 (Day 28) for participants in the immediate intervention arm and after week 8 (Day 56+7 days) for participants in the delayed intervention arm.

Note: Day 1 in the immediate intervention group is defined as the day on which the participant completes the first intervention session with researcher support (guided session). The timing of this first intervention session post randomisation may vary slightly from participant to participant in the intervention arm. Day 1 for participants in the delayed intervention arm will be paired to the timing of Day 1 for participants in the immediate intervention arm, so that the timing of the primary outcome assessment post randomisation will be approximately equal between the two groups.

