- Randomise participants and will issue email/text reminders to participants and study researchers when study-related activities are due.
- Collect intrusive memory diary and intrusive memory rating data during the run-in week and at week 4 (Day 22 to 28) for all participants and at week 8 (Day 50 to 56) for participants in the delayed intervention arm.
- Collect self-reported outcome measurement data at baseline, 4 weeks (Day 28) and 8 weeks (Day 56) in both arms.

The primary comparison will be a between-groups comparison of the number of intrusive memories recorded during week 4 (i.e. from day 22 to 28; which is post intervention in arm 1 and pre-intervention in arm 2), controlling for the number of intrusive memories recorded during the run-in week. Secondary comparisons will be within-group comparisons of the number of intrusive memories in the run-in week (pre-intervention) and week 4 (Day 22 to 28) (post intervention; immediate intervention arm only) and week 4 (Day 22 to 28) (pre-intervention) and week 8 (Day 50 to 56 +7 days) (post intervention; delayed intervention arm only). After the first intervention session, both arms will have continued access to the intervention for the duration of the study period.

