## **9.0 Primary and Secondary Endpoints**

### **9.1 Primary Endpoint**

- Number of intrusive memories of traumatic events recorded by participants in a brief daily online intrusive memory diary for 7 days during week 4 (i.e. from Day 22 to 28 post first intervention session in immediate intervention arm/equivalent timeframe in delayed intervention arm). Analysed as between-group comparison (immediate intervention arm vs. the delayed intervention arm) controlling for the number of intrusive memories during the run-in week.

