### **9.2 Secondary Endpoint**

- Number of intrusive memories recorded by participants in a brief daily online intrusive memory diary for 7 days during the run-in week (pre-intervention) and week 4 (Day 22 to 28) in the immediate intervention arm; and during week 4 (Day 22 to 28) and week 8 (Day 50-56+7 days) in the delayed intervention arm (i.e. within-group comparisons).
- Intrusive memory ratings (distress, disruption to concentration/functioning: how much and how), Impact of Event Scale-Revised (IES-R), PTSD Checklist for DSM-5 (PCL-5) 4-item, Generalised Anxiety Disorder-2-item questionnaire (GAD-2), Patient Health Questionnaire-2-item version (PHQ-2), Sleep Condition Indicator (SCI-08), Physiological Outcome Profile Questionnaire (PSYCHLOPS), World Health Organization Disability Assessment Schedule (WHODAS), 5-level EQ-5D (EQ-5D-5L), Number of sick days, Scale of Work Engagement and Burnout (SWEBO), Intention to leave job at week 4 (i.e. Day 28 post first intervention session in immediate intervention arm/equivalent timeframe in delayed intervention arm) in the immediate intervention arm vs. the delayed intervention arm (i.e. between-groups comparison).
- Intrusive memory ratings (distress, disruption to concentration/functioning: how much and how), Impact of Event Scale-Revised (IES-R), PTSD Checklist for DSM-5 (PCL-5) 4-item, Generalised Anxiety Disorder-2-item questionnaire (GAD-2), Patient Health Questionnaire-2-item version (PHQ-2), Sleep Condition Indicator (SCI-08), Physiological Outcome Profile Questionnaire (PSYCHLOPS), World Health Organization Disability Assessment Schedule (WHODAS), 5-level EQ-5D (EQ-5D-5L), Number of sick days, Scale of Work Engagement and Burnout (SWEBO), Intention to leave job at baseline, 4 weeks (Day 28) and 8 weeks (Day 56) in the immediate intervention arm; and at 4 weeks (Day 28) and 8 weeks (Day 56+7 days) in the delayed intervention arm (i.e. within-group comparisons).

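### The protocol contradicts itself on when the delayed arm's week-8 diary and intrusive memory rating fall; read literally, section 5.7.5 can shorten follow-up after that arm's first session by up to 7 days

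*Protocol*

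**What the plan says.** **Session date.** Protocol 5.7.4 gives the delayed arm's first session as: "On Day 1 of Week 5 (D29+7 days), the participant meets with the researcher (virtual visit) to complete the intervention for the first time". The synopsis footnote explains that the 7 days allow time to arrange this session.

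**Diary without the 7 days.** Protocol 5.7.5 says the delayed arm "will be asked to complete the daily intrusive memory diary during week 8 (D50 to D56) on a daily basis", with the rating at D56. The list in 3.1 of what ePRO collects agrees: "at week 8 (Day 50 to 56) for participants in the delayed intervention arm".

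**Diary with the 7 days.** The synopsis outline says: "In week 8 (Day 50 to 56 +7), they will be asked to complete a daily intrusive memory diary". Section 9.2 has "week 8 (Day 50-56+7 days) in the delayed intervention arm". The synopsis endpoint and analysis lists, the comparison text in 3.1 and section 11.3.4 also add 7 days. The Appendix 1 visit-window row shows the allowance for the delayed arm from week 5 onwards.

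**Within 5.7.5.** The delayed arm's questionnaires and the end of its access carry the 7 days. The diary and rating do not.

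**Immediate arm.** Its post-intervention diary is tied to the participant's own session: "from Day 22 to 28 post first intervention session in immediate intervention arm/equivalent timeframe in delayed intervention arm".

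**SAP.** Table 2 compares week 8 with week 4 for the delayed arm and gives no day range for week 8. Section 5.2.5 models follow-up time with no windowing rule.

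**The concern.** The delayed arm's week-4 to week-8 change in intrusive memories is a stated secondary objective, meant to show the effect of four weeks of access. For the immediate arm the post-intervention week is fixed relative to the session. For the delayed arm it depends on which passage is followed.

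The two places that omit the 7 days are a procedures section and the ePRO collection list, which are the texts most likely to drive the scheduling. The synopsis also sends the reader to section 5.7 for assessment timings by day, so 5.7.5 cannot be set aside as a stray line.

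A diary fixed at D50-56 would be completed after less follow-up by anyone whose session was late. The shortfall would differ between participants and would always run in one direction.

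**Working it through.** **Inputs.** The protocol's day count for the immediate arm is: "Day 1 in the immediate intervention group is defined as the day on which the participant completes the first intervention session". I apply the same count to the delayed arm (an assumption, checked in step 1). Session day s runs from 29 to 36 (5.7.4). The intended window is post-session days 22-28 (9.1, immediate arm). The literal diary is D50-56 (5.7.5).

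**Formulas.**
- Post-session day of study day d = d − s + 1.
- Post-session days 22-28 fall on D(s + 21) to D(s + 27).
- Overlap of D50-56 with that window = 56 − (s + 21) + 1 = 36 − s days.

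**Step 1: reproduce the plan's own figures.** For s = 29, D50 is 50 − 29 + 1 = day 22 and D56 is 56 − 29 + 1 = day 28, as intended. For s = 36, the 28th day is D(36 + 27) = D63, which equals the D56 + 7 that 5.7.4 gives as the end of access. Both agree.

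**Step 2: literal 5.7.5.**

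| First session | D50-56 as post-session days | Days inside 22-28 | Where days 22-28 fall |
|---|---|---|---|
| D29 | 22-28 | 7 of 7 | D50-56 |
| D30 | 21-27 | 6 | D51-57 |
| D31 | 20-26 | 5 | D52-58 |
| D32 | 19-25 | 4 | D53-59 |
| D33 | 18-24 | 3 | D54-60 |
| D34 | 17-23 | 2 | D55-61 |
| D35 | 16-22 | 1 | D56-62 |
| D36 | 15-21 | 0 of 7 | D57-63 |

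Counting elapsed days instead (d − s) lowers every post-session figure by one and leaves the shortfall unchanged.

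**Step 3: the wording with 7 days added.** Two readings are open.
- *One-for-one shift.* A D36 session gives a D57-63 diary, which is days 22-28. There is no mismatch.
- *Wider window, D50 to D63.* A seven-day diary could start on any day from D50 to D57. A D36 session with a D50 start is again days 15-21. A D29 session with a D57 start is days 57 − 29 + 1 = 29 to 63 − 29 + 1 = 35.

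No sentence chooses between these. Appendix 1 note 2 uses the same 7 days in another sense, as a completion window for week-4 and week-8 outcome measures in both arms. The SAP does not settle it.

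**The case against.** The best defence is that the link to the session is already there. The synopsis footnote explains the 7 days as time to arrange the delayed arm's session. Section 5.7.4 gives four more weeks of access ending at D56 + 7, which is four weeks only if the calendar moves with the session. The synopsis also equates four weeks after the first session with Day 56 + 7 for the delayed arm's feedback form. Every passage that defines or analyses this diary endpoint by study day carries the 7 days. On that view 5.7.5 and one line of 3.1 contain an omission, and a shift is the natural reading.

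Much of this stands. A reader might infer that the protocol's rule is a fixed D50-56 diary, so that the delayed arm is by design measured early. The documents do not support that; the endpoint and analysis sections say otherwise. A reader might also infer that four-week recall items such as sick days would reach back before a late session. Section 5.7.5 does not support that either, because it gives the delayed arm's questionnaires the extra 7 days. Plain Day 56 appears only in general statements elsewhere.

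The impact is also limited. Days 15-21 needs the full 7-day slip. The comparison is an uncontrolled within-group one, and the two arms already differ in their pre-intervention week: the run-in week, selected for three or more memories, against week 4.

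The defence does not remove the contradiction within 5.7.5, the synopsis pointer to section 5.7 for timings, or the lack of any statement that the diary days move one-for-one.

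**Conclusion.** The point holds as an internal inconsistency with an unstated anchor. Under literal 5.7.5, follow-up in the delayed arm's post-intervention diary is shortened by 0 to 7 days, and overlap with the intended window falls from 7 of 7 days to none. If the added 7 days are a one-for-one shift, there is no shortfall.

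Only the delayed arm's week-8 assessments, and the week-4 to week-8 within-group secondary comparison that uses them, are exposed. The primary week-4 between-group comparison is untouched. The figures rest on counting the session as day 1 in the delayed arm too. The documents give no distribution of session dates, so the average shortfall cannot be stated. The correction is worth making because the literal text mistimes a named secondary endpoint and the remedy is cheap.

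**What to change.** Reconcile the passages and state one rule: in the delayed arm the week-8 diary covers days 22-28, and the rating and questionnaires fall on day 28, counted from that participant's own first session. In study days this is D50-56 (diary) and D56 (forms), plus the actual lag of 0 to 7 days.

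- Use this wording in the synopsis and in protocol 3.1, 5.7.5, 9.2, 11.3.4 and Appendix 1.
- Align the plain Day 56 statements for the delayed arm in the synopsis outline, 3.1, 3.2 and 9.3.
- Keep the completion window of Appendix 1 note 2 separate from the session lag.
- Give SAP Table 2 the same definition of week 8.
- Have ePRO open the delayed arm's diary from the recorded session date.

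The cost is wording and one ePRO trigger, with no added visits or data items. A delayed participant's final assessment moves by at most 7 days, to D63 at the latest, which the protocol already allows.
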